The principal investigator and co-investigators wish to assure the IRB that any amendments to the protocol or supporting documents will be submitted for approval prior to implementation; problems associated with the research will be reported in accordance with IRB policies.

J. Modifications to Study Protocol and Oversight

Each review will consider whether or not the study should continue without change, be modified, or be terminated. Recommendations regarding modification of the design and conduct of the study might include:

1. Modification of the study protocol based upon review of the safety data;
2. Optional approaches when the incidence of primary study outcomes is substantially less than expected such as recommendations to extend study site;
3. Corrective actions regarding the study site.
4. To assess participant safety, we will have a Data and Safety Officer in place.

The principal investigator and co-investigators will provide oversight, supervision and monitoring of the data collection and will insure integrity of the data which will ultimately ensure subject confidentiality.

K. Monitoring Unanticipated Problems

The principal investigator, [name], will assume responsibility for:

1. Data quality, completeness, and timeliness;
2. Adherence to the protocol;

3. Factors that might affect the study outcome or compromise the confidentiality of the trial data (such as protocol deviations).

The principal investigator will consult with the research team/co-investigators regarding protocol revisions and amendments before adopting such changes. The IRB will be notified of any problems during the conduct of this study.

L. Ensure General Coordination of Study Conduct

The principal investigator agrees to accept responsibility for the scientific conduct of this study and for the rights and welfare of human subjects. General oversight of the coordination of this study will be provided by the principal investigator.

M. Record Retention

All other study related documents (protocols, databases, IRB documents, surveys) will be retained for fifteen (15) years from the date of initial IRB approval and will be kept in the principal investigator's office (University of Kansas School of Medicine - Wichita) under lock and key at the conclusion of this study. At the time of document disposal, documents will be shredded according to KUMC Research Institute Record Retention guidelines. The University of Kansas School of Medicine record retention policy requires research records involving human subjects to be kept for at least 15 years so all data associated with this study will be kept for at least 15 years.

Section V. Results, Source of Funding, and Study Timeline

A. Dissemination of Results

The findings of this study will be submitted to peer reviewed public health and diabetes prevention journals (i.e. American Journal of Public Health, Diabetes, Diabetes Care, Diabetes Obesity and Metabolism, Health Education and Behavior, Maternal Child Health Journal, etc.), and may be presented at conferences (i.e. Society of Behavioral Medicine, American Public Health Association, American Diabetes Association, National Rural Health Association, research forums, ACOG, district meetings, obstetrical updates, etc.). The IRB will be notified at time of continuing review of the research project. Additionally, findings will be used in the future to obtain grant funding and for future intervention development.

B. Source of Funding

This study is funded by the National Institute of General Medical Sciences (NIGMS) in collaboration with the National Heart, Lung and Blood Institute (NHLBI), under award number 5P20GM144269-02S2.

C. Study Timeline (tentative)

The following timeline is suggested for study completion.

Suggested Timeframe	Completed Objective/Goals
October 2023 – November 2023	IRB protocols, preliminary work including hiring of research coordinator, and working with clinical staff at hospital site
November 2024 – March 2024	Finalize planning for participant recruitment
March - May 2024	Start recruitment (rolling recruitment over a 3-month period)
March 2024 – November 2024	Intervention, data collection, preliminary data analysis
November 2024	Intervention/trial closes
November 2024 – December 2024	Final data analysis, manuscript completion, dissemination of findings, preparation for R01 submission
January - February 2025	R01 submission

Section VI. Attachments/Appendices:

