PPOB is a major risk factor for gestational diabetes mellitus (GDM) affecting 7-9% of pregnant women, particularly those with advanced maternal age, low socio-economic status, and women who self-identify as being non-White.⁶ Women with GDM and comorbid conditions such as PPOB experience adverse pregnancy outcomes⁷⁻⁹ including pre-eclampsia,⁹⁻¹¹ emergency cesarean section,^{10,12} maternal prenatal depressive symptoms,¹³ pregnancy hyperglycemia,¹³ and reduced lactation.¹⁴ Further, women with GDM have a seven-fold risk of developing type 2 diabetes mellitus (T2DM) later in life compared to women without GDM.^{15,16}

Lactation is a critical element of postpartum care management. Women who lactate have a lower incidence of T2DM¹⁷⁻²⁰ and reduced postpartum weight.²¹⁻²³ To optimize these benefits, the World Health Organization (WHO)²⁴ and the American Academy of Pediatrics (AAP)^{25,26} recommend exclusive breastfeeding for the first six months of life along with introduction of complementary foods at six months while continuing human milk for up to two years and beyond. About 83% of U.S. women attempt lactation, but only 56% continue to provide human milk with formula supplementation at six months and only 25% provide human milk exclusively at six months.²⁷

Implementation of lifestyle change programs such as the national Diabetes Prevention Program (DPP) can reverse negative effects from PPOB²⁸⁻³¹ and reduce postpartum weight.^{32,33} The DPP, through counseling on effective diet, exercise, and behavior modification, is associated with a reduced risk of developing T2DM by 58%^{34,35} and is shown to be effective for preventing diabetes in women with a history of GDM.³⁶ Yet, access to evidence-based weight management programs that include lactation support remain limited. We posit that a significant number of medically underserved women will elect to participate in DPP-like interventions that include lactation support, if available. Clearly, technology-assisted DPP-like interventions show clinically meaningful weight loss.^{37,38} Extended with lactation support, these programs have still unrealized potential to expand access to medically underserved communities.

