Aim 2: Measure weight loss and duration of lactation through 3 months postpartum among target population. To accomplish this, we will measure pre-pregnancy weight, weight at study entry, weight immediately prior to and after delivery, and weight at specific postpartum time

points. Lactation and infant feeding practices will be measured at similar postpartum time points.

Sample Size and Randomization. The primary outcomes of interest are: (1) to quantify user interest; and (2) to measure weight loss and duration of lactation. Given an anticipated attrition rate of 20%, a total of 50 participants (25 per study arm) will be recruited. The results from this pilot study will be used in sample size estimation for a future study that is sufficiently powered to detect a clinically meaningful effect size. Due to the nature of this project being a feasibility study, the sample size in the proposed study is not based on providing adequate power to detect a clinically meaningful effect size across both study arms. Block randomization with block size of 5 participants will be employed. A sequence of 8 random integers will be generated using a computer algorithm. The first 4 integers of the sequence will be assigned to the DPP plus breastfeeding arm (Tx1); and the last 4 will be assigned to the usual care arm (Tx2). Blocks will be assigned to arms in the increasing order of sequence of integers generated. Study results will be used to determine sample size for a future large-scale RCT that is sufficiently powered to detect a clinically meaningful effect size.

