Aim 2: Measure weight loss and duration of lactation through 3 months postpartum among target population.

- Continuous data will be assessed for normal or skewed distributions. Descriptive statistics such as the mean, standard deviation, median and interquartile range (IQR) will be conducted to summarize outcome measures. To assess for potential bias and evaluate retention, those who complete the trial will be compared to non-completers. Further, Cochran-Mantel-Haenszel tests will be used to reveal associations between categorical/nominal variables after controlling for the strata variables.
- *Weight Loss.* We will measure maternal weight: at baseline, week 30, week 32, week 34 of pregnancy and day 3, day 10, week 3, week 6, month 2, and month 3 postpartum (see Table 4). Pre-pregnancy weight/height will be obtained from medical records.
- *Lactation.* At delivery, initiation of lactation will be measured (defined as starting lactation at birth). We will measure duration of *any* lactation (defined as predominant human milk with formula supplementation) and *exclusive* lactation (defined as human milk exclusively), at specific timepoints (see Table 4). We will also measure formula supplementation when this is first introduced, and quantity/frequency of feedings.

Missing data. Owing to the design of the study and non-transient nature of the study population, we anticipate few to none missing observations. Missing observations will be evaluated for type of missingness. Values missing completely at random or at random will be imputed. Depending on the proportion of missingness, complete case analysis (less than 5% missing) or the multiple imputation method will be used to impute missing data. For longitudinal response (postpartum weight measurements), the last observation will be carried forward to impute the missing response. Results based on imputed data will be compared to findings from complete case analysis, to assess the effect of missingness on study findings.

Comparison of scores on the Breastfeeding Knowledge Assessment, BSES-SF, KPAS,

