Vulnerable populations in this study might include economically/educationally disadvantaged persons. Some pregnant women may be economically and/or educationally disadvantaged based on their demographic profile. We especially want to accommodate these individuals as our study's focus is on measuring postpartum weight and breastfeeding behaviors among an at-risk ethnically and racially diverse, overweight and obese pregnant population.

We will obtain approval from the Ascension Health Institutional Review Board (IRB). With the active assistance of [name], maternal fetal medicine specialist at VCH, [name] and her research coordinator will recruit each participant for the study. All members of the research team involved in consenting and enrolling participants have successfully completed institutional Human Subjects training.

b. Sources of materials

Research material obtained from participants will include: socio-demographic data (i.e. age, race/ethnicity, income, education level, etc.), breastfeeding self-efficacy, breastfeeding knowledge, physical activity level, dietary assessment, maternal sleep, level of postpartum symptoms of depression and anxiety, weight, height, mean arterial blood pressure, blood glucose tolerance level during pregnancy, breastfeeding initiation, breastfeeding duration, use of formula, and solid food. All data are based on validated questionnaires (except for the Breastfeeding Knowledge Assessment questionnaire), and activity and nutrition monitoring as required by the DPP protocol. The validated measures that will be used are the Breastfeeding Self-Efficacy Scale-Short Form (BSES-SF), the Kaiser Physical Activity Survey (KPAS), the Fruit and Vegetable Intake Screener (EATS), the Pittsburgh Sleep Quality Index (PSQI), the Edinburgh Postnatal Depression Scale (EDPS), the Generalized Anxiety Disorder scale (GAD-7), and the Lactation Assessment Care Tool (LACT). These validated survey instruments will be administered at baseline (=study entry) and at study closure (=3 months postpartum) except for the LACT which will be administered within 72 hours of hospital discharge after giving birth. At delivery and through the 3-month postpartum period, we will also obtain the infant's height and weight via healthcare records. Further, at delivery, we will measure if the mother starts breastfeeding and we will measure how long she will continue breastfeeding through 3 months postpartum.

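### Duration of *any* lactation is defined by predominant human milk, so a mother giving some human milk but mostly formula counts in neither category, and the main duration is not named

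*Combined protocol and SAP*

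**What the plan says.** Section III, Sample Size and Randomization, ranks lactation among the main outcomes: "The primary outcomes of interest are: (1) to quantify user interest; and (2) to measure weight loss and duration of lactation". The Aim 2 heading gives the horizon: "Measure weight loss and duration of lactation through 3 months postpartum among target population".

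The Lactation item under Aim 2 is the only place where the durations are defined. There are two: *any* "lactation (defined as predominant human milk with formula supplementation", and *exclusive* "lactation (defined as human milk exclusively), at specific timepoints (see Table 4". No cut-off for *predominant* appears anywhere. The same item adds: "We will also measure formula supplementation when this is first introduced, and quantity/frequency of feedings".

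Table 4 has rows for exclusive human milk, supplemental feeds and solid food at eight timepoints: delivery, discharge, day 7, week 3, month 1, week 6, month 2 and month 3. It has no row for any human milk and none for the date of stopping.

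Section IV.A.b describes the outcome with no condition on how much human milk is given: "we will measure how long she will continue breastfeeding through 3 months postpartum". Section IV.A.a gives follow-up as 6 months after birth; the aims, the design overview and Section IV.A.b say 3 months.

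**The concern.** The label and the definition disagree. *Any* lactation would normally include every mother still giving human milk. Here it requires human milk to predominate, so a mother who has moved to mostly formula but still gives some human milk leaves the category without having stopped. No stopping rule is written, but the definition followed as it stands ends her duration at that change. The wording also does not say that time spent feeding exclusively counts toward *any*, although that is probably meant.

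The outcome is a primary one. Section II.A says that the results will be used to develop a full-scale trial of whether the app lengthens lactation, and Section III says that they will be used to size it. A planning mean and standard deviation for *any* lactation depend on which meaning the analyst uses. With no threshold for *predominant*, two analysts could both follow the text and report different durations for the same mother.

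**Working it through.** **Step 1. The plan's own figure.** Inputs from Section III, Sample Size and Randomization: 50 randomized, 25 per arm, 20% attrition. 50 × (1 − 0.20) = 40 and 25 × (1 − 0.20) = 20 per arm; in reverse, 40/(1 − 0.20) = 50. This reproduces and does not depend on the lactation definition. The 20 per arm is used below.

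**Step 2. Feeding states against the definitions.**

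| Feeding at a timepoint | *Exclusive* | *Any*, as written | Any human milk |
|---|---|---|---|
| Human milk only | yes | not stated, probably yes | yes |
| Mostly human milk, some formula | no | yes | yes |
| Mostly formula, some human milk | no | **no** | yes |
| No human milk | no | no | no |

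The third row is the gap. Section IV.A.b would count that mother as still breastfeeding; the Aim 2 definition would not. The line between the second and third rows cannot be drawn, because *predominant* has no threshold.

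**Step 3. Which duration is the main one.** Under Aim 1 the plan labels its outcomes primary, secondary and tertiary. Under Aim 2 it gives no such labels, and Sample Size and Randomization names duration of lactation without choosing between the two.

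**Step 4. Size, on one assumed history.** The documents give no feeding histories, so this is an illustration on Table 4 timepoints and not a forecast. A mother gives mostly human milk to week 6, then mostly formula with some human milk to month 3. Three months is 91.3/7 = 13.0 weeks.

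- *Any* duration, at-least-predominant reading: 6 weeks.
- *Any* duration, any human milk: 13 weeks (the 3-month limit).
- Shift in the mean of a 20-woman arm per such mother: (13 − 6)/20 = 0.35 weeks.

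With k such mothers the shift is 0.35k weeks. The documents do not give k. If 10% to 30% of the 20 had this history (an assumption), k is 2 to 6 and the shift is 0.7 to 2.1 weeks. The at-least-predominant duration can never exceed the any-human-milk duration, so the arm mean can only be shortened. The difference between arms moves only if the arms differ in such mothers.

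**Step 5. Mothers lost before 3 months.** Planned loss is 0.20 × 25 = 5 per arm; how many would be lactating at last contact is unknown. The general rule is "Values missing completely at random or at random will be imputed", with complete-case analysis when under 5% is missing and multiple imputation otherwise. Loss of 20% is above 5%, so imputation would apply. For a mother lost while lactating, the duration is known to be at least the time to last contact. Nothing in the rule makes use of that lower limit.

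**Step 6. Stopping date.** If only feeding status at each timepoint is recorded, stopping is known only to the gap between timepoints. The largest gap, month 2 to month 3, is (91.3 − 60.9)/7 = 4.3 weeks.

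**The case against.** The strongest reply is that this is an unpowered feasibility study. Aim 2 plans descriptive summaries and names no between-arm test of duration. Both durations will be measured. The timing of first formula and the amount and frequency of feeds are also collected, so a duration of any human milk may be derivable. All of that stands, and it limits the point: this is a definition to correct, not a demonstrated loss of data. It does not remove the point, because the written definition would still direct the analyst to the shorter duration, and the estimate is wanted for planning.

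A reader might infer more than the documents support:

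- *That exclusive feeders score zero on* any. The words can be read so, but a cumulative meaning is more natural. The wording needs clarifying; it does not show an error in the numbers.
- *That the primary duration will be picked after the data are seen.* Both are to be measured, so the unnamed main duration is a lesser matter.
- *That mothers still lactating at 3 months have no valid value.* The outcome is duration through 3 months, which is fully observed for anyone followed that long. Only earlier loss raises the question of censoring.
- *That the imputation plan is unchecked.* The Missing data paragraph also compares imputed with complete-case results.
- *That Hispanic participants are especially affected.* Section I.F says that Hispanic women often supplement with formula, which the *any* definition covers. It does not say that they feed mostly formula.
- *That the eMOMS 1.0 means show how many would lactate past 3 months.* Section I.C does not say which duration those means describe or where lactation follow-up ended, and it calls the results preliminary.

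**Conclusion.** The point holds in this form, as something that should be fixed. The stated definition of *any* lactation is wrong for its label, lacks a threshold, leaves out mothers giving some human milk but mostly formula, and conflicts with Section IV.A.b. The main duration is not named for a primary outcome.

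The size is 0.35 weeks of arm mean per affected mother. That rests on 20 completers per arm, the assumed history and the at-least-predominant reading; a different history gives a different figure. The number of affected mothers is unknown, so the total effect on the planning estimate is unknown too. The sample size of this trial is not affected.

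**What to change.** 1. Define *any* lactation as any human milk regardless of other feeds, with exclusive feeders included. Keep *exclusive* as human milk only. If *predominant* is wanted, report it as a separate category with a stated threshold.
2. Name the duration of *any* lactation through 3 months as the main lactation outcome, which agrees with Section IV.A.b.
3. At each of the eight Table 4 feeding timepoints, record whether any human milk was given (yes/no) and the date of the last human-milk feed. The list of appendices names no feeding form, so check what the form in use already captures.
4. For mothers lost before 3 months while still lactating, treat duration as censored at last contact. A Kaplan-Meier estimate with its mean restricted to 3 months would do; with complete follow-up it equals the plain mean. It assumes that loss is unrelated to stopping, which should be stated.
5. Reconcile the 6 months in Section IV.A.a with the 3 months used elsewhere.

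The cost is a few sentences, two fields at existing timepoints and slightly more analysis. No visits are added and the sample size does not change. The fields should be in place before feeding data are collected, because a last-feed date that was not recorded may not be recoverable.

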Self-Administered Surveys and Incentive to Participate. At recruitment and at study closure, participants will complete seven survey instruments; each of which assesses women's physical activity, nutrition, mental health, maternal sleep, breastfeeding knowledge, and breastfeeding experience (see Appendices 4 through 12). Those randomized to Tx2 will complete all survey instruments and outcome measures, as are those randomized to the intervention (Tx1). All surveys will be self-administered (see Appendices 4 through 12) and are available in English. The pre- and post-survey instruments are identical. They will be administered electronically at baseline (at study entry) and at three months postpartum (see Table 4. Outcomes Measures, under Section III). Via email, the study coordinator will provide each participant with a REDCap link that provides electronic access to each survey. Informed consent will occur when the participant opens the survey. Participants will self-administer the survey and may stop at any time. Potential survey participants will have the option of contacting researchers with any questions prior to completing the survey. The survey instrument will be set up using REDCap and responses will be automatically entered and stored in REDCap for data analysis. All identifying information will be removed from the data prior to analysis. Research personnel will not have access to any identifying information contained in the survey.

At recruitment and at study closure 3 months postpartum, all participants will complete six pre- and post-survey instruments: (1) Questions on socio-demographic characteristics and health status (will only be asked at study entry/baseline) (Appendix 4); (2) Breastfeeding Knowledge (Appendix 5); (3) Breastfeeding Self-Efficacy Scale-Short Form (BSES-SF)

(Appendix 6);⁹³⁻⁹⁶ (4) Kaiser Physical Activity Survey (KPAS) (Appendix 7);^{97,98} (5) the Eating At America's Table Study (EATS) Fruit & Vegetable Intake Screener⁹⁹⁻¹⁰¹ (Appendix 8); and (6) the Pittsburgh Sleep Quality Index (Appendix 9). Each instrument will take about 10-15 minutes to complete and participants are provided with adequate time (i.e., about 1 hour) to complete all surveys.

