Additionally, recent evidence shows that higher BMI pregnant women may have an increased likelihood of depressive and anxiety symptoms.^{102,103} Therefore, at specific timepoints (see Table 4. Outcome Measures, under Section III), all participants will complete the Edinburgh Postnatal Depression Scale (EPDS) (Appendix 10)¹⁰⁴⁻¹⁰⁶ and the General Anxiety Disorder-7 (GAD-7) scale (Appendix 11).¹⁰⁷ Each scale takes about 5 minutes to complete. If a participant has an elevated score for depressive or anxiety symptoms, then the participant will be referred to The Village, a mental health clinic in Wichita, Kansas, or their own mental health care provider if the participant has one. [name] research coordinator will ask the study participant if she can contact staff at The Village on her behalf and provide them with the participant's name and phone number. Licensed mental health therapists at The Village will then call the participant and attempt to schedule an appointment. Participants will sign a release form at consent allowing [name] and her team to follow up with The Village to record the rate at which participants are referred and attend at least one appointment.

Last, upon delivery and within 72 hours of hospital discharge, the participant will complete the Lactation Assessment Care Tool (LACT) (Appendix 12). The LACT identifies families at risk for breastfeeding difficulty and facilitates access to the most effective level of care.¹⁰⁸ All study survey instruments/scales are listed in Table 3.

Table 3. Survey Instruments

Study Instrument	Items Measured	No. of Items	Reliability	Populations Validated
Socio-Demographic Characteristics and Health Status	To collect data on the study sample.	24 items; multiple choice and select all that apply	Not yet performed.	Not yet performed.
Breastfeeding Knowledge Assessment	To assess knowledge of breastfeeding (44 items), to assess socio-demographic characteristics (6 items), to assess health status (7 items)	57 items; multiple choice, and Likert-type scale	Not yet performed.	Not yet performed.
Breastfeeding Self-Efficacy Scale-Short Form (BSES-SF)	To assess levels of self-efficacy in postpartum women. BSES-SF has also been used with prenatal women.	14 items; 5-point Likert-type scale.	Cronbach's alpha = 0.97	Postpartum women at 1 week, 4 weeks, and 8 weeks.

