Physical Activity and Dietary Intake	Kaiser Physical Activity Survey (KPAS) ^{97,98}	X										X
	Fruit and Vegetable Intake Screener (EATS) ⁹⁹⁻¹⁰¹	X										X
Mental Health Screening	Edinburgh Postnatal Depression Scale (EPDS) ^{104,106}	X										X
	Generalized Anxiety Disorder Scale (GAD-7) ¹⁰⁷	X										X
Maternal Sleep	Pittsburgh Sleep Quality Index (PSQI)	X										X
Infant Measures												
Growth	Infant weight, length, head circumference (per vaccination schedule by WHO) ¹¹⁰				X	X	X	X	X	X	X	X
Feeding Practices*	Exclusive human milk feedings				X	X	X	X	X	X	X	X
	Supplemental infant feedings (i.e., formula, water, juice, etc.)				X	X	X	X	X	X	X	X
	Solid food feedings (i.e., cereal, baby food)				X	X	X	X	X	X	X	X
Lactation Assessment	Breastfeeding Self-Efficacy Scale – Short Form (BSES-SF) ⁹³	X										X
	Lactation knowledge survey	X										X
	Lactation Assessment Care Tool (LACT)					X						

*Note: Data on feeding practices are collected at these timepoints due to (1) congruent child-wellness visits to the primary care provider, and (2) having an established human milk supply and return-to-work by the parent at 3 and 6 weeks of life.

As this is a pilot trial, we will also collect the following data: number of women screened, number of women recruited and enrolled, number of participants who withdraw from the study and reasons for withdrawal, number of participants who complete the DPP protocol, and number of participants who complete the breastfeeding sessions. Upon recruitment into the study and at study closure, all participants will complete the BSES-SF, KPAS, EATS, PSQI, LACT, EPDS, and GAD-7 to assess differences in knowledge and self-efficacy toward breastfeeding, physical activity, mental health, maternal sleep, and nutrition. Table 4 shows a timeline for data collection in both study arms.

Aim 1: Quantify interest in use of the DPP-lactation support app among target population. To accomplish this, we will: (1) measure research engagement including rates of screening, recruitment, and retention among users, especially rural and racially/ethnically diverse women; (2) assess barriers/facilitators to enrollment/retention through surveys and semi-structured in-depth interviews or focus groups; and (3) evaluate intervention uptake, delivery, and adherence via tracking/measuring use of the app.

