EATS, and PSQI. The Breastfeeding Assessment is based on 44 questions. Cronbach's alpha will be used to test the internal consistency of the data. The "difference in Breastfeeding Assessment scores between recruitment and at study closure" in both study arms will be assessed using the multiple linear regression approach. The model will be adjusted for the effect of age, race/ethnicity, level of education, annual household income, family history of diabetes, pre-diabetes status, and parity. The BSES-SF score is based on 14 questions and ranges from 14 to 70 points. Cronbach's alpha will be used to test the internal consistency of the data. The "difference in BSES scores between recruitment and at study closure" across both study arms

will be assessed using the multiple linear regression approach. The model will be adjusted for the effect of age, race/ethnicity, level of education, annual household income, family history of diabetes, pre-diabetes status, and parity. The KPAS score comprises of 38 questions that are distributed sequentially but non-uniformly across four sections and measure household and family care activities (household index); occupational activities (occupational index); active living habits (active living index); and participation in sports and exercise (sports and exercise index). For each section, Cronbach's alpha will be used to test the internal consistency of the data. For each index of physical activity, "difference/change between recruitment and at study closure" across both study arms will be assessed using the multiple linear regression approach after adjusting for the effect of the previously stated covariates. The EATS survey consists of 10 questions and the PSQI consists of 10 questions. For each question, counts and percentages will be reported for participants at recruitment and at study closure across both study arms. For each survey item, count and percentages will be reported. The difference in scores for each survey instrument across both study arms will be assessed using a multiple linear regression approach adjusted for the effects of demographic and health status variables.

Section IV. Patient Protections and Methods to Minimize Risk

A. Risks to Human Subjects

a. Human Subjects Involvement, Characteristics, and Design

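### The questionnaire comparisons use each baseline score only by subtraction; adding it as a covariate would usually give narrower intervals from data already collected

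*Combined protocol and SAP*

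**What the plan says.** The relevant text is the paragraph on comparison of scores near the end of Section III. Its heading names five instruments: Breastfeeding Knowledge, BSES-SF, KPAS, EATS and PSQI.

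- **Breastfeeding Knowledge and BSES-SF.** The outcome is the difference between recruitment and closure, analysed by linear regression "adjusted for the effect of age, race/ethnicity, level of education, annual household income, family history of diabetes, pre-diabetes status, and parity".
- **KPAS.** For each index the outcome is the "difference/change between recruitment and at study closure", with the same covariates.
- **EATS and PSQI.** Counts and percentages are given per question. The only model is the closing sentence: "The difference in scores for each survey instrument across both study arms will be assessed using a multiple linear regression approach adjusted", where the adjustment is for demographic and health status variables.
- **EPDS and GAD-7.** The heading does not name them. They are reached only if the closing sentence's reference to each instrument extends beyond the five. The text after Table 4 does list the "EPDS, and GAD-7 to assess differences in knowledge and self-efficacy toward breastfeeding, physical activity, mental health, maternal sleep, and nutrition", so a comparison of some kind is intended.

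The baseline scores exist. Section IV.A.b says "These validated survey instruments will be administered at baseline (=study entry) and at study closure (=3 months postpartum) except for the LACT", Table 4 shows the same two time points (and adds the lactation knowledge survey), and Section II.F & G has both arms complete everything.

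**The concern.** No covariate list names the baseline score of the instrument being analysed. The phrase about health status does not supply it: Section II.F & G describes that as a separate item, "Questions on socio-demographic characteristics and health status (will only be asked at study entry/baseline", with its own appendix and its own row in Table 3.

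A change score does use baseline, but it forces the baseline slope to be 1. If k is the baseline SD divided by the month-3 SD and r is the correlation between visits, the actual slope of month-3 score on baseline is r/k. When r/k is below 1, subtraction over-corrects any chance difference between arms at entry. Such differences are not small here: with 20 per arm, the baseline mean difference has a standard deviation of √(2/20) = 0.32 score SDs. Over repeated randomisations the over-correction averages to zero, so there is no bias. It does add noise, and the reported intervals are then wider than they need to be.

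**Working it through.** **Sample size.** Section II.C and the sample size paragraph of Section III give 50 randomised, 25 per arm, with 20% attrition: 50 × 0.80 = 40, or 20 per arm, as stated. No power or effect size is stated for these outcomes, so there is no further figure to reproduce.

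**Assumptions.** The documents do not give r, k or the coding of the covariates. I take r = 0.3, 0.5, 0.7 and k = 0.8, 1, 1.25, both after the planned covariates. The seven covariates are coded as q = 10 terms: age 1, race/ethnicity 2, education 2, income 2, family history 1, pre-diabetes 1, parity 1.

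**Variance per woman**, in units of the month-3 variance:
- change score: k² + 1 − 2rk
- baseline score as a covariate: 1 − r²
- difference: (k² + 1 − 2rk) − (1 − r²) = (k − r)², which is never negative

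**Cost of estimating the slope.** With 40 women, an intercept, arm and q other terms, the average inflation is 1/(36 − q): 1/26 = 3.8% for q = 10, and 1/36 = 2.8% for q = 0.

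**Expected variance ratio** (baseline covariate ÷ change score) = (1 − r²)/(k² + 1 − 2rk) × (1 + 1/26):

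| k | r = 0.3 | r = 0.5 | r = 0.7 |
|---|---|---|---|
| 0.8 | 0.815 | 0.927 | 1.018 |
| 1 | 0.675 | 0.779 | 0.883 |
| 1.25 | 0.521 | 0.593 | 0.652 |

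Example, k = 1 and r = 0.5: 0.75/1.00 × 1.038 = 0.779. Simulation with 40,000 trials per cell gave 0.675, 0.775 and 0.884 for the k = 1 row. Taking square roots of that row, intervals are about 18%, 12% and 6% narrower.

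**When it does not help.** The ratio exceeds 1 when (k − r)² < (1 − r²)/26. At r = 0.5 that means |k − 0.5| < √(0.75/26) = 0.17, so k between about 0.33 and 0.67. At r = 0.7 it means |k − 0.7| < √(0.51/26) = 0.14, so k between about 0.56 and 0.84. The full average cost of 3.8% applies at k = r, where the true slope is 1.

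**Spread of that cost in a single trial.** The inflation is t²/(38 − q), where t measures the chance imbalance in the baseline score and has 38 − q degrees of freedom.
- q = 10: 95th percentile 2.048²/28 = 15%. The inflation exceeds 3.8% in about 31% of trials.
- q = 0: 95th percentile 2.024²/38 = 11%.

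**If the closing sentence means month-3 scores alone.** The ratio before slope cost is 1 − r² = 0.91, 0.75, 0.51, so the covariate helps on that reading too.

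**The case against.** The strongest reply is that the plan already handles baseline by taking change scores. That gives a valid estimator, and choosing between two valid estimators is a matter of preference in a study whose sample size is expressly not based on power. This largely stands, and it is why the point is minor. It does not remove the point: the plan commits to these regressions with 95% intervals and two-sided 0.05 tests, and already spends degrees of freedom on seven other covariates.

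Two further objections also stand in part. The size of the gain rests on assumed r, k and q, and particular care is needed for questionnaires given before and after birth, where SDs may differ. And 20 per arm is a completer count, while the plan is intention-to-treat with imputation. If all 50 women were fully observed, the slope cost would be 1/(50 − 4 − 10) = 1/36 = 2.8%, and the k = 1 row would be 0.668, 0.771, 0.874, so little changes.

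A reader might infer more than the documents support:
- *That the comparison is biased, or that baseline is ignored.* It is neither; baseline enters by subtraction.
- *That adding the covariate can cost at most about 4%.* That figure is an average, and a single trial can lose more.
- *That this is a safety gap for depression and anxiety.* The heading does not name the EPDS or GAD-7, so it is unclear whether this model applies to them. Individual care does not depend on the regression: "If a participant has an elevated score for depressive or anxiety symptoms, then the participant will be referred to The Village".

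**Conclusion.** The point holds as a minor matter of precision. For Breastfeeding Knowledge, BSES-SF and the KPAS indices, baseline enters by subtraction and not as a covariate. The closing sentence most naturally does likewise for EATS and PSQI, and for the EPDS and GAD-7 if it is meant to cover them.

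On the stated assumptions with equal SDs, the planned analysis gives up about 32%, 22% and 12% of variance at correlations of 0.3, 0.5 and 0.7. With unequal SDs the range is wider, from roughly half the variance to a loss of about 2% in the cases tabulated. The documents cannot say which case applies to which instrument. No decision rule in the plan turns on these intervals.

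**What to change.** In the comparison-of-scores paragraph of Section III:

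1. Add the words 'and the baseline score of the same instrument' to the covariates for every instrument scored at both visits. The LACT is not among them, since Table 4 schedules it only at discharge.
2. State whether the closing sentence covers the EPDS and GAD-7.

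The outcome wording need not change. Once the baseline score is in the model, the month-3 score and the change score give the same arm difference, because subtracting a covariate from the outcome only shifts that covariate's own coefficient by 1. This also settles what the closing sentence means by a difference in scores.

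No new data, visits or staff are needed. The price is one degree of freedom per model. On the assumed coding the model then has 13 parameters (intercept, arm, ten terms, baseline score) for 40 women, leaving 27 residual degrees of freedom in place of 28. If that seems crowded, dropping some of the seven listed covariates is a reasonable separate choice.
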